3.9.5 Assessment of Suicidality

[figure not shown]
ABC-Irritability (ABC-I) subscale scores (Aman et al., 1985) will be summarized descriptively at Baseline and all post-Baseline study visits by treatment group. Change from Baseline and percent change from Baseline to all post-baseline study visits will also be summarized descriptively by treatment group. The Aberrant Behavior Checklist – Community (ABC-C) Baseline Record Form version 23Apr2018 and the Follow Up Record Form version 20Apr2018 will be implemented.

[figure not shown]
All ABC-I assessment results will be included in a subject listing.

3.9.6 Seizure Diary Data

The number of subjects reporting a new type of seizure during treatment and the type of new seizures reported during treatment will be summarized. Additionally, the seizure frequency per 28 days (normalized) will be calculated for the following study periods: Baseline (Screening to Day -1), Week 6 (Day 1 to Week 6 visit date or EOT before Day 43), and Week 12 (Week 6 visit date + 1 day to Week 12 visit date or EOT between Day 44 and Day 85). Percent change in seizure frequency per 28 days from Baseline to all post-baseline study visits also will be summarized descriptively by treatment group.

All seizure diary results will be included in a subject listing.

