Dosing will be initiated at the starting dose for the first 5 days. On Day 6, tolerability will be assessed by the investigator. If there are no tolerability concerns (e.g., excessive somnolence, dizziness, vomiting, negative behavior changes) and no AE related to the study drug has been observed since Day 1 by the LAR/caregiver or the investigator, then the dose of OV101 will be increased to the maintenance dose for the duration of the study. The maintenance dose identified at screening will remain consistent throughout the study. If tolerability concerns are observed on Day 6, the subject will discontinue study drug.

[figure not shown]
The subject's maintenance dose for the duration of the study will be set based on the subject's weight at the screening visit, and the subject should continue taking the maintenance dose after the Day 6 assessment until the EOS. Tolerability will again be assessed during the Day 11 phone call while the subject is taking the maintenance dose. The investigator may initiate down-titration on Day 11 by 1 capsule (Table 2) based on investigator assessments of tolerability and AEs, or medical necessity. If down-titration is initiated, then the investigator should reassess tolerability with the modified dose regimen within 3 days of the dosing change. No further changes in dose regimen should be made after Day 15.

[figure not shown]
If tolerability is not acceptable at any other time during the 12 weeks of treatment, the investigator should discuss the situation with the medical monitor or his/her delegate. Any intolerability must be documented as an AE. The daily dose may not be lower for any subject than the reduced maintenance dose indicated in Table 2. If a subject cannot tolerate the reduced maintenance dose, that subject must discontinue treatment. Any dose adjustments or changes in dosing must be documented in the electronic case report form and supporting rationale must be documented in the medical record or other appropriate source document.

Sample Size:

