4.2 Discontinuation and Withdrawal of Subjects

Subjects who discontinue treatment during the study will be encouraged by investigators to continue to participate in all scheduled study site visits and assessments, and study data will be collected for these subjects per protocol. Study drug administration may be stopped early at the discretion of the investigator (or designee) if a subject does not tolerate the dosing regimen. Every effort should be made to keep subjects in the study.

Early withdrawal of a subject from the study (before Week 12) will initiate procedures for ending all subject participation in the study, including EOT and EOS assessments (Section 4.2.2). For subjects who are withdrawn early, an EOT visit should be conducted within 2 weeks after the last day of study drug. After completing the EOT visit, an EOS phone visit should be completed within 2 weeks after completing the EOT visit. The duration of the study is defined for each subject as the date signed written informed consent is provided through the EOS phone visit. The Sponsor may continue to enroll subjects to account for discontinuations, withdrawals, early terminations, etc.

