6.4.2.2 Seizure Diary

The seizure diary is a caregiver-reported clinical outcome assessment measure that captures the total number and duration of seizures. Caregivers will record the number, duration, and type of seizures each day using the paper seizure diary. Also, refer to Section 6.4.1.1 for AE reporting criteria for these seizure events.

The caregiver will be trained by the site with specific instructions beginning with the screening visit to ensure compliance in recording seizures. The seizure diary will be completed each day during 12 weeks of treatment beginning at screening and continuing through the EOT. Seizure diaries will be collected and reviewed by the investigator with the subject's caregiver for proper recording at the baseline, Week 6, and Week 12 (or EOT) study site visits. Seizure Identification Form and Diagnostic Review Forms (SIF/DRF) will be completed by site personnel for every eligible subject. This information will be faxed or emailed to The Epilepsy Study Consortium (TESC) for review and approval. The SIF/DRF will be used to ensure that the seizures are

classified accurately. SIF and DRF forms will be collected for patients who have enrolled/completed the study if feasible.

For the prospective baseline period, the seizure frequency (expressed as a 28-day frequency) will be calculated as

$$(\# \text{ of seizures}) / (\# \text{ of days seizures were assessed}) \times 28$$

Seizure frequency calculated through this method will be used to confirm the eligibility.

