7.9.5 Seizure Diary Data

Seizure diary data will be summarized descriptively at baseline and all post baseline study visits by treatment group. Additionally, the seizure frequency (expressed as a 28-day frequency) will be calculated for the following study periods: Baseline (Screening to Day 1), Week 6 (Day 1 to Week 6 visit date), and Week 12 (Week 6 visit date + 1 to Week 12 visit date). Percent change in seizure frequency from baseline to all post baseline study visits also will be summarized descriptively by treatment group.

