3.1.8 Analysis Visit Windows

Visit windows for study conduct are specified in Table 1: Schedule of Activities. Unless otherwise specified, the following analysis visit rules will be implemented for all endpoints [REDACTED] and seizure diary (see sections 3.8.3, 3.8.4, and 3.9.6 for analysis visit window computations). For all unscheduled visits and end of treatment (EOT) visits from subjects discontinuing treatment early (before Week 12), assessments will be mapped according to the analysis visit windows in Table 2 for primary summarization and analysis. If the visit does not fall within any of the analysis visit windows, then the visit will be considered missing at the specified time point for analysis purposes.

Table 2: Nominal (Targeted) Time Points and Analysis Visit Windows

Assessment	Nominal (Targeted) Time Point	Analysis Visit Window (Interval in Study Days)
Baseline Assessments	Study Day 1	≤ Day 1
Phone/Titration (Day 6)	Study Day 6	>Day 1 - ≤Day 8
Phone/Titration (Day 11)	Study Day 11	≥Day 9 - ≤Day 21
Week 6 (Study Day 43)	Study Day 43	≥Day 22 - ≤Day 64
Week 12 (Study Day 85)	Study Day 85	≥Day 65 - ≤Day 92
Week 14 (Study Day 99)	Study Day 99	≥Day 93

After mapping the data from unscheduled and end of treatment (EOT) visits from subjects discontinuing treatment early to the nominal time point, the following rules will apply if multiple records are available within a single analysis visit window unless otherwise specified for a particular analysis:

- If a record exists for the nominal time point, that record will be selected for analysis.
- If a record for the nominal time point does not exist and multiple records are available within a single analysis visit window,
 - The record closest to the planned assessment day will be selected for analysis
 - If 2 records are equidistant from the target day, then the earliest record will be selected (does not apply to the Week 12 or 14 visits).
- If a subject has no record in an analysis window, the subject will be considered missing at that time point.

For the primary and key secondary objectives, a supportive analysis will be conducted in which CGI-I-AS assessments from unscheduled visits and end of treatment (EOT) visits from subjects discontinuing treatment early (before Week 12) will be mapped according to the analysis visit windows in Table 3.

Table 3: Nominal (Targeted) Time Points and Alternative Analysis Visit Windows

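### SAP 3.9.6 ends the seizure-frequency periods at a visit or an undefined EOT instead of at last dose, so early stoppers' rates can mix on-drug and off-drug days and some early stops have no defined period

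*SAP*

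**What the plan says.** Percent change in 28-day seizure frequency from baseline is a named safety endpoint (Protocol 7.2.2, SAP 3.3.6). SAP 3.9.6 sets the two treatment periods:

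- First period: "Week 6 (Day 1 to Week 6 visit date or EOT before Day 43".
- Second period: "Week 12 (Week 6 visit date + 1 day to Week 12 visit date or EOT between Day 44 and Day 85".

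Protocol 7.9.5 has only visit dates: "Week 6 (Day 1 to Week 6 visit date), and Week 12 (Week 6 visit date + 1 to Week 12 visit date". It has no rule for early stoppers, so it does not settle what the SAP leaves open. SAP 3.1.8 (one sentence partly blacked out) refers the seizure diary to 3.9.6 for its windows, so Table 2 does not settle it either.

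Four other statements decide which diary days enter these periods:

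- The diary is kept daily, "beginning at screening and continuing through the EOT" (Protocol 6.4.2.2).
- For children withdrawn early from the study, "an EOT visit should be conducted within 2 weeks after the last day of study drug" (Protocol 4.2).
- "Subjects who discontinue treatment during the study will be encouraged by investigators to continue to participate in all scheduled study site visits and assessments" (Protocol 4.2).
- "If tolerability concerns are observed on Day 6, the subject will discontinue study drug" (Protocol synopsis and 5.2.1), so an exposure of about five days is foreseeable.

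**The concern.** A seizure rate is a count divided by days. If the period runs past the last dose, off-drug days enter both parts, and the figure is no longer the rate on drug. For completers the Week 12 visit is the end of treatment, so they contribute almost no off-drug days. The mixing falls on children who stopped early, whose tolerability is of most interest.

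It can act in either direction. If seizures rise on drug and settle after stopping, the rate is diluted. If stopping provokes seizures, they are charged to the treatment period.

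Separately, if the bounds do not cover every stopping day, the programmer must choose a period after the fact or leave diary days out of a safety endpoint. Seizures are an adverse event of special interest (SAP 3.9.1.6), so this summary should be unambiguous before unblinding.

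**Working it through.** The plan gives no figure to reproduce. The check sets possible stopping days against the period bounds.

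**Inputs.** L is the last-dose day. g is the lag from last dose to the EOT visit, 0 to 14 days (Protocol 4.2, children withdrawn early). The Week 6 visit is taken at its target, Day 43 (SAP Table 2). EOT is read as the visit. The diary is assumed complete to the end of the period.

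**Mixing in the first period.** Off-drug share = g / (L + g). As an illustration, assume the true seizure rate on drug is twice the off-drug rate. The ratio shown is then (2L + g) / (L + g), against a true 2.00.

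| Last dose | Lag | EOT | Off-drug share | Ratio shown |
|---|---|---|---|---|
| Day 5 | 7 | Day 12 | 7/12 = 58% | 17/12 = 1.42 |
| Day 5 | 14 | Day 19 | 14/19 = 74% | 24/19 = 1.26 |
| Day 14 | 7 | Day 21 | 7/21 = 33% | 35/21 = 1.67 |
| Day 14 | 14 | Day 28 | 14/28 = 50% | 42/28 = 1.50 |
| Day 28 | 7 | Day 35 | 7/35 = 20% | 63/35 = 1.80 |
| Day 28 | 14 | Day 42 | 14/42 = 33% | 70/42 = 1.67 |

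At zero lag there is no mixing. In counts, three seizures on Days 1 to 5 and none later give 3/5 × 28 = 16.8 per 28 days on drug. As planned they give 3/12 × 28 = 7.0 (7-day lag) or 3/19 × 28 = 4.4 (14-day lag).

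The reverse case: if the drug does nothing but the rate doubles after stopping, last dose on Day 5 with a 14-day lag shows (5 + 2 × 14)/19 = 1.74 against a true on-drug ratio of 1.00.

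**Mixing in the second period.** Off-drug share = 14 / (L − 43 + 14) at the 14-day lag. Last dose on Day 50 gives 14/21 = 67%, Day 57 gives 14/28 = 50%, and Day 71 gives 14/42 = 33%.

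**Stopping drug but staying in visits.** If the visit dates end the periods and the diary continues to Week 12, a child whose last dose is Day 5 has Days 6 to 43 off drug. That is 38/43 = 88% of the first period and 100% of the second. With last dose on Day 28 the first-period share is 15/43 = 35%, and the second is again 100%.

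**Coverage of the bounds.**

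- Day 43: the first rule needs an EOT before Day 43 and the second starts at Day 44. An early EOT on Day 43 fits neither. It can arise from last doses on Days 29 to 43.
- After Day 85: last doses on Days 72 to 84 can give an EOT on Days 86 to 98, past the second bound.
- No Week 6 visit: the second period starts the day after that visit. A child who misses it but reaches Week 12 has no end for the first period and no start for the second. The same holds for an early EOT on Days 44 to 85 without a Week 6 visit.

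Over L = 1 to 84 and g = 0 to 14 there are 84 × 15 = 1,260 combinations. Of these, 15 fall on Day 43 and 91 after Day 85, so 106 (8.4%) have no period. This counts date combinations and does not forecast children.

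**The case against.** The strongest reply is that EOT in 3.9.6 may mean the date treatment ended. The abbreviation list expands it as end of treatment, and 3.9.6 says visit date for visits but plain EOT for early stoppers. On that reading the mixing disappears wherever EOT closes the period, and the gap after Day 85 is largely moot. The Day 43 gap and the missed Week 6 visit remain. So does the question of which date governs when a child has both an early EOT and later visits. The visit reading is better supported: Protocol 4.2 schedules EOT as a visit, SAP 3.1.8 speaks of "end of treatment (EOT) visits from subjects discontinuing treatment early (before Week 12", and SAP 3.7.1 and 3.7.2 name the last dose date when they mean it. Still, it is a reading, and the undefined term is part of the defect.

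A 14-day tail also matches the SAP's window for treatment-emergent events (3.9.1), so a combined period could be deliberate. But extra days dilute a rate in a way they do not dilute a count of children with an event, and the SAP states no such intention.

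A reader might infer that worsening would be hidden. The documents do not support that. A clear rise over baseline, a new seizure type or status epilepticus must be reported as an adverse event (Protocol 6.4.1.1), seizures are tabulated as events of special interest, and all diary results are listed.

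A reader might also combine the Day 6 rule with the two-week EOT rule and conclude that such a child has EOT by Day 19. The first concerns stopping drug, the second withdrawal from the study. Protocol 4.2.2 asks treatment stoppers for EOT assessments where possible, without that timing. The Day 5 rows therefore describe a child who is also withdrawn, and 14 days is the maximum lag.

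Finally, a late EOT might be recorded as the Week 12 visit, whose date has no Day 85 cap. Remote visits under the pandemic addendum still have a date, so the Week 6 problem arises only when no visit takes place.

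**Conclusion.** The point holds. Neither period is cut at last dose, EOT is undefined, and the bounds are not contiguous. On the visit reading, a child withdrawn early contributes 0 to 14 off-drug days, which is 58% of the period at a 7-day lag and 74% at the maximum for a last dose on Day 5. A child who stays in visits after stopping can have periods mostly or wholly off drug.

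The consequence is limited. The analysis is descriptive, no alpha or sample size is touched, and the same seizures reach other outputs. What suffers is one named safety summary. It is a cheap improvement worth making.

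Three stronger inferences are not supported:

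- That the distortion will fall more on OV101. The only figures are Phase 2 discontinuations for adverse events (placebo 1, once daily 0, twice daily 3), and this trial doses once each evening. Direction and any arm difference are unknown.
- That about 10 of 90 children are expected to stop. The documents set a target of at least 80 evaluable children, which is not a dropout forecast.
- That an EOT after the Week 6 visit but before Day 43 is a further gap. The first period can end at that EOT, so the days are covered and no second period is needed.

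**What to change.** In SAP 3.9.6:

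- Define EOT (visit date or last-dose date).
- End each on-drug period at the earlier of the visit date and the last dose date.
- Split at the Week 6 visit date, or at Day 43 if that visit was missed.
- Assign all later on-drug days to the second period, with no Day 85 cap.
- Summarise diary days after last dose separately, by arm.
- Show the number of diary days beside each rate.
- Keep the visit-based summary as supportive if wanted.

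The cost is SAP wording and light programming. Last-dose dates and daily diary entries are already collected, and no dosing or stopping rule changes. The downside is unstable rates for very short exposures: one seizure in 5 days becomes 1/5 × 28 = 5.6 per 28 days, and a few such values could pull an arm mean. Showing the diary days makes this visible but does not remove it, so the planned medians and quartiles should be read alongside the means.

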Vital signs, weight, and body mass index will be summarized descriptively at baseline and all post baseline study visits by treatment group. Change from baseline to all post baseline study visits will be summarized descriptively by treatment group.

Physical examinations (general appearance; skin; head, ear, eye, nose, and throat; neck; lymph node; chest; heart; abdominal cavity; limb; central nervous system; and musculoskeletal) at baseline will be summarized. Shifts from baseline to post baseline study visits in each body system/site will be summarized by treatment group.

Suicidality and seizure diary data will be summarized descriptively at baseline and all post baseline study visits by treatment group. Change from baseline to all post baseline study visits also will be summarized descriptively by treatment group.

List of Abbreviations

Abbreviation	Definition
ABC-I	Aberrant Behavior Checklist-Irritability subscale
AE	adverse event
ANCOVA	Analysis of Covariance
ANOVA	Analysis of Variance
AS	Angelman syndrome
[REDACTED]	
β-hCG	beta-human chorionic gonadotrophin
BID	twice daily
CFR	Code of Federal Regulations
[REDACTED]	
CGI-I	Clinical Global Impressions-Improvement
CGI-I-AS	Clinical Global Impressions-Improvement-Angelman syndrome
CGI-S-AS	Clinical Global Impressions-Severity-Angelman syndrome
[REDACTED]	
CSR	clinical study report
CTSC	Clinical Trial Steering Committee
eCRF	electronic case report form
EDC	electronic data capture
EMA	European Medicines Agency
EOS	end of study
EOT	end of treatment
FAS	full analysis set
FDA	Food and Drug Administration
GABA	gamma-aminobutyric acid
GCP	Good Clinical Practice
ICF	informed consent form
ICH	International Council for Harmonisation
IDMC	Independent Data Monitoring Committee
IEC	independent ethics committee
IRB	institutional review board
LAR	legally acceptable representative
[REDACTED]	
MedDRA	Medical Dictionary for Regulatory Activities

Abbreviation	Definition
MMRM	Mixed Model Repeated Measures
	
PPS	per protocol set
QD	once daily
SAE	serious adverse event
SAP	statistical analysis plan
SIF/DRF	Seizure Identification Form and Diagnostic Review Form
SS	safety set
TEAE	treatment-emergent adverse event
	
Ube3a	ubiquitin protein ligase E3A
UBE3A	ubiquitin protein ligase E3A gene
ULN	upper limit of normal
VABS-3	Vineland Adaptive Behavior Scale, 3 rd Edition

Definition of Terms

Term	Definition
Day 1	The first day of study drug administration
ELARA	Study OV101-18-002, an open-label extension study

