7.2.2 Safety Endpoints

- Incidence of AEs
- Change in clinical laboratory parameters from baseline to each post baseline assessment
- Shift in clinical laboratory parameters from baseline to each post baseline assessment
- Change in vital sign measurements from baseline to each post baseline assessment
- Shift in physical examination parameters from baseline to each post baseline assessment
- Change in suicidality assessment (ABC-I) from baseline to each postbaseline as assessed by ABC-I. The ABC-I will serve as a surrogate measure for suicidality
- Percent change in seizure frequency (expressed as a 28-day frequency) from baseline to each post baseline timepoint

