1 INTRODUCTION

Study OV101-19-001 is a Phase 3, multicenter, double-blind, placebo-controlled, parallel-group study. The goals of the study are to evaluate the efficacy and safety of once each evening (QHS) OV101 (gaboxadol) compared to placebo in pediatric individuals with Angelman Syndrome (AS).

The statistical analysis plan (SAP) contains a detailed description of the data presentations and statistical analyses that will be included in the clinical study report (CSR) for Protocol OV101-19-001 version 4.0, 19 June 2020. The statistical methods and analyses described here are based on those presented in Section 7 of the study protocol.

This study is ongoing during the Coronavirus Disease 2019 (COVID-19) pandemic, and as a result, there are expected to be protocol deviations related to COVID-19, including virtual visits (visits conducted remotely via visiting nurse, audio only, or audio and video) instead of clinic visits and use of local labs. Data will be collected as closely as possible to the Schedule of Assessments (Table 1), and analysis will be performed using the observed data.

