3.3.6 Safety Endpoints

- Incidence of adverse events
- Change in clinical laboratory parameters from Baseline to each post-baseline assessment
- Shift in clinical laboratory parameters from Baseline to each post-baseline assessment
- Change and shift in vital sign measurements from Baseline to each post-baseline assessment

- Change in suicidality assessment (ABC-I) from Baseline to each post-baseline assessment. The ABC-I will serve as a surrogate measure for suicidality
- Percent change in seizure frequency (collected in seizure diary) per 28 days from Baseline to each post-baseline time point

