3.9 Safety Analysis

All safety analyses will be based on the SS. Descriptive statistics will be used to summarize all safety endpoints by treatment group. Data summaries will be displayed for incidence of TEAEs, clinical laboratory variables, vital signs, body weight and body mass index, physical examinations, clinical assessment of suicidality (ABC-I) and seizure diary data.

Unless otherwise specified below, safety data for subjects 2 to 3 years old (inclusive) will only be presented in listings and will be displayed in by-subject graphs, as appropriate.

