4.2 Computation of Derived Data

4.2.1 Time Points and Duration

Standard calculations used across many assessments:

- Changes from baseline = Post Baseline value – Baseline value
- Percentage change from baseline = [(Post Baseline value – Baseline value)/Baseline Value]*100.

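### The SAP's only by-arm seizure-frequency summary is percent change, which is undefined for children with no baseline seizures; the protocol's zero-safe diary summaries are not carried over

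*SAP*

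**What the plan says.** SAP 3.9.6 plans two diary summaries. One counts children reporting a new seizure type. The other follows a calculation of 28-day frequency for Baseline, Week 6 and Week 12: "Percent change in seizure frequency per 28 days from Baseline to all post-baseline study visits also will be summarized descriptively by treatment group". The endpoint list in SAP 3.3.6 likewise names only "Percent change in seizure frequency (collected in seizure diary) per 28 days from Baseline to each post-baseline time point". SAP 4.2.1 gives the formula: "Percentage change from baseline = [(Post Baseline value – Baseline value)/Baseline Value]*100". No readable text says what happens when the baseline value is zero.

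The protocol plans more. Its endpoint in 7.2.2 is also percent change ("Percent change in seizure frequency (expressed as a 28-day frequency) from baseline to each post baseline timepoint"), but 7.9.5 opens with a separate commitment: "Seizure diary data will be summarized descriptively at baseline and all post baseline study visits by treatment group". The statistical methods in the synopsis plan the same visit summaries and add, for suicidality and seizure diary data together, "Change from baseline to all post baseline study visits also will be summarized descriptively by treatment group". Both of these are defined at zero.

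SAP 3.9 keeps a general line that data summaries will be shown for several safety topics, including "clinical assessment of suicidality (ABC-I) and seizure diary data", without naming a diary measure or visit. SAP 1 states: "The statistical methods and analyses described here are based on those presented in Section 7 of the study protocol".

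**The concern.** Protocol 2.5 and SAP 2.1 both name seizure diary data within the safety objectives. The protocol's introduction gives a reason to look closely: in STARS, seizure and myoclonic epilepsy were among the events more frequent on OV101 than on placebo, and serious seizure events occurred in two OV101-treated subjects.

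Zero baselines are foreseeable. Protocol 4.1.2 excludes poorly controlled seizures, and no readable criterion sets a minimum seizure count. SAP 3.5.1 has history categories for children with no seizures ever and for those with none in the last two years.

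A percent change from zero does not exist, so these children leave the by-arm frequency table. The arms can then look alike even if more previously seizure-free children have seizures on drug. SAP 3.1.2 would show a smaller n and a missing count, but it would not separate a zero baseline from a lost diary, which mean very different things.

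**Working it through.** The plan states no figure on this point, so there is none to reproduce. The check compares the texts, applies the formula, and then illustrates the mechanism with assumed numbers.

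**1. Measures named by arm**

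| Source | Observed frequency by visit | Absolute change | Percent change |
|---|---|---|---|
| Protocol synopsis | yes (diary data) | yes | no |
| Protocol 7.2.2 | no | no | yes |
| Protocol 7.9.5 | yes (diary data) | no | yes |
| SAP 3.3.6 | no | no | yes |
| SAP 3.9.6 | calculated; by-arm summary not stated | no | yes |
| SAP 3.9.5 (ABC-I, for contrast) | yes | yes | yes |

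**2. The formula at zero.** For a baseline of 0 and a later value of 0, 1, 4 or 28 per 28 days, percent change is undefined every time. Absolute change is 0, 1, 4 and 28.

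**3. Children left in the summary.** SAP 2.2.1 plans about 45 per arm. With zero-baseline share s (assumed), the evaluable number is 45 × (1 − s): 36, 27, 18 and 9 for s = 20%, 40%, 60% and 80%.

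**4. Children who do have seizures can also record zero.** Under an assumed Poisson count, P(zero) = exp(−rate × days/28).

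| Rate per 28 days | 14 diary days | 28 diary days |
|---|---|---|
| 0.25 | 88% | 78% |
| 0.5 | 78% | 61% |
| 1 | 61% | 37% |
| 2 | 37% | 14% |
| 4 | 14% | 2% |

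A longer baseline, which the pandemic addendum allows, lowers these shares. At 42 days they are exp(−0.75) = 47% at a rate of 0.5 and exp(−1.5) = 22% at a rate of 1.

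**5. Invented example, 45 per arm.** In each arm 25 children go from 4 to 3 and 20 start at zero. Of those 20, 5 on OV101 and 1 on placebo rise to 2; the rest stay at zero.
- Percent change: (3 − 4)/4 = −25% in both arms, n = 25 each.
- Mean absolute change: OV101 (5×2 − 25)/45 = −0.33; placebo (1×2 − 25)/45 = −0.51; difference +0.18.
- Zero-to-any: 5/20 = 25% against 1/20 = 5%; difference 20 points, Newcombe 95% CI −3.2 to 42.3, Fisher p = 0.18.

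**6. Why the zero-to-any count needs the placebo arm.** At an unchanged rate, the chance of at least one seizure over 84 treatment days is 1 − exp(−3 × rate): 53%, 78% and 95% at 0.25, 0.5 and 1 per 28 days. Some zero-baseline children will have seizures on treatment by chance alone.

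**7. Precision of that count.** For 30% against 10%, the Newcombe 95% CI for the difference is −16 to 51 points with 10 zero-baseline children per arm, −5 to 43 with 20, and −0.5 to 39 with 30.

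**The case against.** The strongest reply is that leaving a summary out of SAP 3.9.6 does not cancel it. SAP 3.9 promises diary summaries, SAP 1 bases the methods on Protocol Section 7, and the word *also* in 3.9.6 can be read as adding percent change to a frequency table. This is a fair reading, and the SAP was written against protocol version 4.0, whose wording may differ. But none of these lines names a measure or visit, whereas SAP 3.9.5 spells out all three measures for ABC-I. The protocol shares the fault, since its own endpoint is percent change and absolute change appears only in the synopsis.

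Second, restoring the protocol's summaries would barely expose the problem. This stands. In the example, absolute change has the same minimum (−1), quartiles (−1 and 0), median (−1) and maximum (+2) in both arms; only the means differ, and both suggest improvement. The zero-to-any table does most of the work. It is an addition that neither document planned, and it will be imprecise.

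Third, other routes exist. Under Protocol 6.4.1.1 a clear increase, a new type or status epilepticus is a reportable event. Investigators review the diaries, doubtful events should be reported, and SAP 3.9.1.6 tabulates seizure events by arm. A first seizure in a child with no seizure history would count as a new type on any reading; a recurrence after a quiet baseline might not, because the term is undefined. These routes reduce the loss. They do not replace a by-arm diary measure, because the adverse-event route depends on an event being judged reportable, while the diary is kept daily for every child. Subject listings do not compare arms.

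**Conclusion.** The concern holds. As written, SAP 3.9.6 commits to one by-arm seizure-frequency measure, and it cannot include a child whose baseline is zero. The protocol's visit summaries and the synopsis's absolute change, both defined at zero, are not specified there.

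The size in this trial is unknown because neither the zero-baseline share nor the seizure rates are given. The shares, Poisson rates, diary lengths and example arms above are assumptions that show the mechanism only. The consequence is limited to a descriptive safety summary: no hypothesis test, alpha or primary result depends on it, and adverse-event tables would catch part of any signal. It should still be corrected, because the omitted children are those in whom new or returning seizures are of most interest.

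**What to change.** In SAP 3.3.6 and 3.9.6, for safety-set children aged 4 to 12:

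1. Summarize observed 28-day frequency by arm for Baseline, Week 6 and Week 12, and absolute change for the two post-baseline periods.
2. Tabulate by arm the zero-baseline children with at least one diary seizure on treatment, with the difference from placebo and its confidence interval. Add counts of children with an increase, no change and a decrease.
3. Restrict percent change to non-zero baselines, show that n, and count zero-baseline children separately from those with a missing diary.
4. Reconcile the synopsis, Protocol 7.2.2, Protocol 7.9.5 and SAP 3.9.6 so that they name the same measures.

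The cost is SAP wording, an aligning protocol edit and one or two descriptive tables from diary data already collected. The zero-to-any count should be presented as descriptive, given its width at about 45 per arm.
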